
Framingham Risk Equation
 
 • The predicted probability, \hat{p}, of having a cardiovascular disease (CVD) within the next 10-years according to the Framingham formula [D’Agostino, 2008] is 
For females:
 $\hat{p}_F = 1 - S_0(t)^{\exp\{ 2.32888 \times \log(\text{age}) + 1.20904 \times \log(\text{TC}) - 0.70833 \times \log(\text{HDL}) + 2.76157 \times \log(\text{SBP}_u) + 2.82263 \times \log(\text{SBP}_t) + 0.52873 \times I_s + 0.69154 \times I_d - 26.1931\}}$ 
For males:
 $\hat{p}_M = 1 - S_0(t)^{\exp\{ 3.06117 \times \log(\text{age}) + 1.12370 \times \log(\text{TC}) - 0.93263 \times \log(\text{HDL}) + 1.93303 \times \log(\text{SBP}_u) + 1.99881 \times \log(\text{SBP}_t) + 0.65451 \times I_s + 0.57367 \times I_d - 23.9802\}}$

Demographics and Baseline Characteristics

Where

$$S_0(t) = \begin{cases} 0.95012, & \text{females} \\ 0.88936, & \text{males} \end{cases}$$

$$I_s = \begin{cases} 1, & \text{current smoker} \\ 0, & \text{otherwise} \end{cases}$$

$$I_d = \begin{cases} 1, & \text{diabetic} \\ 0, & \text{otherwise} \end{cases}$$

TC = total serum cholesterol (mg/dL),

HDL = serum HDL cholesterol (mg/dL),

SBP_u = systolic blood pressure (mmHg) if participant is not treated for high blood pressure (note that if a participant is treated for high blood pressure then log(SBP_u) = 0)

SBP_t = systolic blood pressure (mmHg) if participant is treated for high blood pressure (note that if a participant is not treated for high blood pressure then log(SBP_t) = 0)

- A participant will be considered as treated for high blood pressure if during screening it has specified that is suffering from hypertension. A participant is classified as diabetic if current or past is indicated in the medical conditions eCRF for Type 1 or Type 2 diabetes mellitus, or if baseline (Day 1) fasting glucose ≥7.00 mmol/L (126 mg/dL) and HbA1C >6.5%.
- Smoking status is collected in the eCRF at Day 1. A current smoker is defined as currently smoking/using tobacco or has smoked/used tobacco within the previous 6 months; a former smoker is defined as previously smoked/used tobacco products and has not smoked/used tobacco products within the previous 6 months.

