- This calculation will not be performed for participants who have indicated current or past myocardial infarction conditions on the eCRF. These participants will not be included in summary statistics of risk, but they will be counted in the highest category of risk in the summary by category.
- Framingham Risk will also be calculated at Month 6 and Month 12.
 - Baseline smoking status will be used for the Month 6 calculation. Smoking status collected at Month 12 will be used for the Month 12 calculation.
 - Diabetic status is defined as:
 1. Current or past is indicated in the medical conditions eCRF for Type 1 or Type 2 diabetes mellitus, or
 2. At any time prior to and including the analysis timepoint:
 - 2a. fasting glucose ≥7.00 mmol/L (126 mg/dL) and HbA1C >6.5%, or
 - 2b. an adverse event is collected as having “type 1 or type 2 diabetes mellitus”
 - “Treated for high blood pressure” at Month 6 and Month 12 is defined as
 1. hypertension at baseline or
 2. use of medication treating hypertension which started prior to and including the analysis time point

Lipid-modifying Agents

- The following ATC codes correspond to lipid-modifying agents:
 - ATC Level 2: C10
 - ATC Level 3: C10A, C10B (if Level 2 is not available)

Demographics and Baseline Characteristics

 ○ ATC Level 4: C10AA, C10AB, C10AC, C10AD, C10AX, C10BA, C10BX (if level 2, 3 are not available) ● Participants are considered to have used a lipid-modifying agent at baseline if they are taking the medication at the time of their baseline fasting lipid testing date. ● Participants are also considered to have used a lipid-modifying agent at baseline if they stopped their lipid modifying medication within 12 weeks prior to their baseline fasting lipid testing date.
Treatment Compliance

 ● For defining protocol deviation (i.e. treatment non-compliance) leading to exclusion from the Per Protocol population, the total non-compliance days will be calculated (see details in Section 16.1). The percentage of the total number of non-compliant days to the Exposure ('overall exposure' for CAB+RPV treatment) will be used to define protocol deviation leading to exclusion from PP Population for the Month 12 analysis due to study treatment non-compliance (i.e. >10%).
Adherence to CAB/RPV Injection Schedule

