3.60.	Safety	VS1	Summary of Anthropometric Parameters by Visit (Lipid Evaluable)	Q2M and BIK only. Include all planned visits Include: weight, height, BMI, waist and hip circumference, CCI and Tanita scale measurements (total body Fat %, bone mass, muscle mass, TBW%)	M6
3.61.	Safety	VS1	Summary of Anthropometric Parameters by Visit Excluding Subjects with Cosmetic procedures (Lipid Evaluable)	Q2M and BIK only add footnote: Cosmetic procedures include procedures of the torso/thighs (exclude face/neck) including but not limited to liposuction/liposculpture/implants.	M12
3.62.	Safety	VS1	Summary of Change from Baseline in Anthropometric Parameters by Visit (Lipid Evaluable)	Q2M and BIK only Same parameters as 3.60	M6

Safety: Tables					
No.	Population	GSK Standard/ Example Shell	Title	Programming Notes	Deliverable [Priority]
3.63.	Safety	VS1	Summary of Change from Baseline in Anthropometric Parameters by Visit Excluding Subjects with Cosmetic Procedures (Lipid Evaluable)	
Q2M and BIK only
 
add footnote:
 
Cosmetic procedures include procedures of the torso/thighs (exclude face/neck) including but not limited to liposuction/liposculpture/implants.
	M12

Safety: Tables					
No.	Population	GSK Standard/ Example Shell	Title	Programming Notes	Deliverable [Priority]
Metabolic Syndrome					
3.64.	Safety	SAF_T15	Summary of Percent of Subjects with Metabolic Syndrome and Risk Factors (Maintenance Phase)	
Q2M and BIK only
 
In addition to Metabolic syndrome, also include percentage for each of the 5 factors:
 
Elevated waist circumference; Elevated triglycerides; Reduced HDL-C; Elevated blood pressure; Elevated fasting glucose
	M6, M12
3.65.	Safety	SAF_T12	Summary of Shift in Metabolic Syndrome and Risk Factors at M12 (OLI and BIK) /M11(D2I) from Baseline	
Update to M5/6 for M6 RE. Q2M and BIK only.
 
Shift table from baseline to M5/6 or M11/12, Yes/No/Missing
	M6, M12
3.66.	Safety	SAF_T10	Statistical Analysis of Proportion of Subjects with Metabolic Syndrome at M12 (OLI and BIK) /M11(D2I) – Logistic Regression		M6, M12

Safety: Tables					
No.	Population	GSK Standard/ Example Shell	Title	Programming Notes	Deliverable [Priority]
Cardiovascular Risk and Substance Use					
3.67.	Safety	207966/primary_15/T1.22	Summary of Cardiovascular Risk Assessments by Visit (Maintenance Phase)	Add section header for each visit. For month 6, only calculate Framingham equation For month 12, also include smoking status Q2M vs. BIK	M6, M12

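### The Framingham rule sets treated blood pressure status from a hypertension diagnosis, and differently at baseline than at Months 6 and 12, so some predicted risks and risk changes in Safety Table 3.67 are wrong

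*SAP*

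**What the plan says.** SAP section 16.6.2 (Framingham Risk Equation) prints a 10-year risk formula for each sex. Systolic pressure enters through one of two terms. SBP_u is "systolic blood pressure (mmHg) if participant is not treated for high blood pressure", and SBP_t is "systolic blood pressure (mmHg) if participant is treated for high blood pressure". The term that does not apply is set to zero.

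The rule for choosing the term at baseline is: "A participant will be considered as treated for high blood pressure if during screening it has specified that is suffering from hypertension". It does not refer to medication.

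The risk is recalculated at Months 6 and 12 under a different rule. A participant then counts as treated through either of two routes. The first is "hypertension at baseline or"; the second is use of an antihypertensive started by the analysis time point.

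The result is reported in Safety Table 3.67, "Summary of Cardiovascular Risk Assessments by Visit (Maintenance Phase)", for Q2M and BIK at the Month 6 and Month 12 deliverables.

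**The concern.** The equation separates participants by treatment; the rule that feeds it separates them by diagnosis. The two differ for anyone with hypertension who is not taking a drug for it, and for anyone taking a drug without the diagnosis having been recorded at screening.

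Two consequences follow. First, a participant with untreated hypertension at entry is given too high a risk at baseline, and at each later visit while still untreated. If that participant starts a drug on study, the coding does not change because it was already set to treated. Only the lower pressure enters, so the score drops.

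Second, medication counts on study but not at baseline. Status can therefore change between visits with no change in the participant.

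At stake is whether a by-visit table of cardiovascular risk can be read as change over time.

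**Working it through.** The plan states no numerical result here, so there is no figure to reproduce. The check applies the printed equations.

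**Inputs from section 16.6.2**
- Systolic coefficients, untreated / treated: men 1.93303 / 1.99881 (difference 0.06578); women 2.76157 / 2.82263 (difference 0.06106).
- Baseline survival S0: men 0.88936; women 0.95012.
- Risk = 1 − S0^exp(LP), where LP is the linear predictor.

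**Assumed profiles (not in the document)**
- A: man aged 50, total cholesterol (TC) 200 mg/dL, HDL 45 mg/dL.
- B: either sex, age 50 unless stated, TC 190 mg/dL, HDL 50 mg/dL.
- Both are non-smokers without diabetes.

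**1. Inflation from coding an untreated person as treated.** Hazard multiplier = exp[(b_treated − b_untreated) × ln SBP].
- Men: exp(0.06578 × ln 130) = 1.377; at 140 mmHg, 1.384.
- Women: exp(0.06106 × ln 130) = 1.346; at 140 mmHg, 1.352.
- Profile A at 140 mmHg: 14.3% under the plan, 10.6% if coded untreated.

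**2. Starting a drug on study, profile A, 150 to 130 mmHg.** The non-pressure part of LP is 3.06117 ln 50 + 1.12370 ln 200 − 0.93263 ln 45 − 23.9802 = −9.6013.
- Untreated at 150: 1.93303 ln 150 = 9.6857, LP = 0.0844, risk 12.0%.
- Coded treated at 150: 1.99881 ln 150 = 10.0153, LP = 0.4140, risk 16.3%.
- Treated at 130: 1.99881 ln 130 = 9.7293, LP = 0.1280, risk 12.5%.

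Actual treatment status gives 12.0% to 12.5% (hazard × 1.04). The plan gives 16.3% to 12.5% (hazard × 0.75).

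**3. When the sign is wrong.** With actual status, the score falls only if the treated pressure is below exp[b_untreated × ln(SBP0) / b_treated], where SBP0 is the pressure before treatment.

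| Starting SBP | Break-even, men | Drop needed | Break-even, women | Drop needed |
|---|---|---|---|---|
| 140 | 119.0 | 21.0 | 125.8 | 14.2 |
| 150 | 127.2 | 22.8 | 134.6 | 15.4 |
| 160 | 135.4 | 24.6 | 143.4 | 16.6 |

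Smaller drops give a rise with actual status and a fall under the plan. Larger drops give a fall both ways, but too large a one under the plan. Change in risk for profile B, in percentage points:

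| Case | Actual status | Plan's rule |
|---|---|---|
| Man, 140 to 130 | +1.67 | −1.61 |
| Man, 150 to 120 | −1.08 | −4.82 |
| Woman, 140 to 130 | +0.54 | −1.39 |
| Woman, 150 to 130 | −0.62 | −2.96 |

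The pattern holds at other ages. For a man going from 150 to 130, the changes are +0.23 against −1.78 at age 40, and +0.70 against −5.23 at age 60.

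**4. The opposite mismatch.** Take a participant on an antihypertensive at entry for whom hypertension was not specified at screening. Read literally, this person is untreated at baseline and treated at Months 6 and 12. For profile B at an unchanged 130 mmHg, risk moves from 7.94% to 10.78% (man) or from 4.67% to 6.23% (woman).

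**The case against.** The strongest reply is that little depends on this. Table 3.67 is a descriptive summary with no model or test specified for the score. The same rule applies to both randomised arms, so baseline inflation is balanced in expectation. Blood pressure is also shown directly: vital signs by visit (Table 3.56), and the elevated blood pressure component of metabolic syndrome and its shift (Tables 3.64 and 3.65). Concomitant medications are summarised in Table 1.21. All of this stands, and it is why the point is minor.

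It also rules out a stronger reading. A reader might infer that an arm with more new or worsening hypertension that is then treated would show falling risk, so that the table hides a signal. The document does not support this:
- A participant without hypertension at baseline who starts a drug moves to the treated coefficient through the medication route, as the equation requires.
- Hypertension that arises on study and stays untreated is not coded as treated.
- In a participant already coded as treated, a rise in pressure still raises the score.
- A false or overstated fall needs four things together: hypertension specified at screening, no antihypertensive at entry, a drug started on study, and pressure below the Day 1 value.
- The mismatch in step 4 works in the other direction, so no net direction of bias is established.

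The reply does not rescue the rule itself. A diagnosis is not a forced substitute for treatment, because the Month 6 and 12 rule already uses medication. The hypertension covariates in sections 8.4.2 and 8.5.2 also name history and medication as separate items. Those covariates accept past use, so they show that the data exist rather than supply a ready definition of current treatment.

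**Conclusion.** The rule is wrong as written. It chooses the treated coefficient by diagnosis where the plan's own equation calls for treatment, and its baseline and on-study definitions differ.

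For participants with untreated hypertension at entry, the hazard is too high by a factor of about 1.38 (men) or 1.35 (women) at 130–140 mmHg while they remain untreated. If they start a drug and pressure falls below Day 1, the fall in risk is overstated. From a starting pressure of 140–160 mmHg, it has the wrong sign for drops under about 21–25 mmHg in men and 14–17 mmHg in women. An artificial rise is possible for participants on a drug at entry without a recorded diagnosis.

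The multipliers and break-even pressures depend only on the printed coefficients and the systolic pressure. The risk percentages rest on the assumed profiles. The document does not say how many participants fall into either group, so the effect on arm summaries in Table 3.67 cannot be sized. The primary endpoint is unaffected. Severity: minor.

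**What to change.** In section 16.6.2, replace both rules with one definition for Day 1, Month 6 (Month 5 for D2I) and Month 12 (Month 11 for D2I). A participant counts as treated for high blood pressure if an antihypertensive medication, started on or before the assessment, is ongoing at it according to the concomitant medication records. Remove the hypertension diagnosis as a sufficient criterion, both at baseline and on study. Requiring ongoing use also closes a gap in the current medication route, which asks only that the drug was started.

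The cost is one sentence in the SAP and one derived medication flag. No new data are needed, and no table other than 3.67 changes.

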02*	
For Month 12 analysis only:
 
Participant has non-compliance with IP (including IM dosing errors) or took/received incorrect IP (i.e., other than the one to which they were randomized) up to an analysis timepoint of interest, meeting the following conditions during the Maintenance Phase:
 
 1. Two or more injection intervals affected by over dosage deviations, for example 
 • Extra injection or excessive volume administered • Length of time between injections less than 21 days between the first and second injections (between M1 and M2 for OLI; between Day 1 and M1 for D2I), or less than 52 days for all subsequent dosing intervals, excluding split doses up to the analysis visit of interest (M12 for OLI /M11 for D2I) 
* 21 = 28 – 7; 52 = 28 + 31 – 7 (smallest possible dosing interval allowed – 7 days)
 2. At least 10% of total time on-treatment with under dosing deviations in the Maintenance Phase up to the analysis visit of interest (i.e. Month 12 for OLI and BIK/Month11for D2I), where the % of non-compliance is calculated as: (total number of non-compliant dosing days / total number of intended exposure days) * 100%

Number	Exclusion Description

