	
Where :
 
 • Total number of intended exposure days = date of the last analysis timepoint snapshot viral load (up to Injection Study Day 372 for OLI subjects, up to Study Day 372 for D2I subjects and up to Study Day 378 for BIK subjects) – Start Date of Study Treatment + 1 • Total number of non-compliant dosing days up to the analysis timepoint visit (or date of IP discontinuation/ withdrawal, whichever is earlier), is derived as follows: BIK Arm: 
 ○ Duration of interruptions in BIK arm for reasons other than treatment-related adverse events/laboratory abnormalities (based on Exposure eCRF forms) Q2M Arm: 
 ○ Length of time (in days) in excess until next injection from date of dosage/administration deviation potentially resulting in under dosage. Examples include: 
 - less than 3 ml administered - early stop of oral bridging prior to the next planned injection ○ Length of time (in days) in excess beyond 31 days between the first and second injections and beyond 69 days for all subsequent dosing intervals. 
 * 69 = 31+ 31 + 7 (largest possible dosing interval allowed + 7 days) - For those with oral bridging (OB), length of time (in days) is calculated between the start of oral bridging and the preceding injection ○ Interrupted days in oral study treatment (oral lead-in or oral bridging) if the oral dose has been interrupted for 3 or more consecutive days and the primary interruption reason is not adverse event or laboratory abnormality (based on the eCRF Exposure forms). 3 days will be assumed if such interrupted days are not available in the database.
03	
Prohibited medications: receiving ART medication other than that prescribed/allowed by the study (excluding permanent changes in ART regimen; such cases will be retained as 'HIV1-RNA ≥ 50 c/mL' in the per protocol snapshot analysis) or receiving prohibited concomitant medication that would impact exposure or response to therapy with duration and route of administration taken into consideration, as recorded in the Protocol Deviation form in the eCRF based on study team review (where indicated in the PDMP as case-by-case determination)

04	
Permanent discontinuation of IP/withdrawal due to a reason of "Protocol Deviation" (as recorded in the eCRF Conclusion form).

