Exposure to CAB + RPV (oral lead-in) = * Q2M OLI subjects only	Oral lead-in CAB/RPV Stop Date – Oral lead-in CAB/RPV Start Date +1
Exposure to CAB LA + RPV LA =	Number of IP injections received during Maintenance Phase up to and include the Month 12 (OLI) or the Month 11 (D2I) injection
Overall Exposure to IP (Q2M OLI) =	min [Date of latest Maintenance Phase visit up to and including Month 14 (OLI), max (Date of last CAB LA + RPV LA injection +67, Date of last oral CAB/RPV dose)] – Oral lead-in CAB/RPV Start Date +1
Overall Exposure to IP (Q2M D2I) =	min [Date of latest Maintenance Phase visit up to and including Month 13(D2I), max (Date of last CAB LA + RPV LA injection +67, Date of last oral CAB/RPV dose)] – CAB LA + RPV LA Start Date +1
Overall Exposure to Study Treatment (OLI) =	min [Date of latest Maintenance Phase visit up to and including Month 14, max (Date of last CAB LA + RPV LA injection +67, Date of last oral CAB/RPV dose, Date of last oral SOC bridging)] – Oral lead-in CAB/RPV Start Date +1
Overall Exposure to Study Treatment (D2I) =	min [Date of latest Maintenance Phase visit up to and including Month 13, max (Date of last CAB LA + RPV LA injection +67, Date of last oral CAB/RPV dose, Date of last oral SOC bridging)] – CAB LA + RPV LA Start Date +1
Maintenance Phase: BIK arm	
Exposure = Min (Date of latest Maintenance Phase visit up to and including Month 13, Maintenance Phase Treatment Stop Date, Date of Maintenance Phase Discontinuation) – Maintenance Treatment Start Date + 1	

 ◦ Last oral dose may be CAB/RPV or SOC ART Oral Bridging where CAB/RPV is not available due to COVID-19 ◦ Last CAB LA + RPV LA injection / last oral dose is only applicable to participants who permanently discontinue from study 	

Corrected QT (QTc)

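### Section 16.6.2 restates the Per-Protocol non-compliance rule with a denominator that can run past the endpoint, unlike Appendix 1, which is the defining text

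*SAP*

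**What the plan says.** **Appendix 1 (Section 16.1.1), exclusion category 02, Month 12 only.** A participant is a candidate for exclusion with "At least 10% of total time on-treatment with under dosing deviations in the Maintenance Phase". The percentage is "total number of non-compliant dosing days / total number of intended exposure days". Intended exposure runs from treatment start to the "date of the last analysis timepoint snapshot viral load (up to Injection Study Day 372 for OLI subjects", with caps at Study Day 372 for D2I and Study Day 378 for BIK. The numerator is the "Total number of non-compliant dosing days up to the analysis timepoint visit", or to the date of discontinuation or withdrawal if that is earlier.

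**Section 16.6.2, Treatment Compliance.** The reader is sent to Section 16.1 for the count of non-compliant days. The section then gives its own ratio, "The percentage of the total number of non-compliant days to the Exposure" (overall exposure for CAB+RPV), and its own cut-off for exclusion, "due to study treatment non-compliance (i.e. >10" per cent.

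**Section 16.6.4, Extent of Exposure.** For OLI, overall exposure is bounded by the "Date of latest Maintenance Phase visit up to and including Month 14 (OLI"). For D2I and BIK the corresponding visit is Month 13. In Q2M participants who permanently discontinue, the last injection plus 67 days also enters. Two versions of overall exposure are defined, one to IP and one to study treatment including SOC bridging. Section 16.6.2 does not say which it means, and it does not cite Section 16.6.4.

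**Which text defines the PP set.** The PP row of Section 4 refers to Section 4.1 and Appendix 1 for the deviations that exclude a participant, and Section 4.1 refers on to Appendix 1. Appendix 1 introduces its list as the defining criteria and makes each exclusion subject to case-by-case clinical determination.

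**The concern.** One exclusion is written down twice, with a different inequality and a different denominator. Under Section 16.6.2 the numerator stops at the Month 12/11 visit while the denominator may go on to Month 13/14. Time after the endpoint, during which no non-compliant day can be counted, therefore dilutes the percentage. The dilution differs by arm because the next scheduled visit is about 60 days later in Q2M and 28 days later in BIK. It also depends on whether a Month 13/14 visit is in the data. Section 3.2 triggers the primary analysis once everyone has completed Month 12/11, so two participants with identical dosing up to the endpoint could receive different percentages.

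The PP analysis is a planned consistency check on the primary and key secondary non-inferiority comparisons (Sections 5.5.2, 5.5.3 and 7.1.5.1). Its population should follow from one rule, and that rule should not be looser in the test arm merely because of the visit calendar.

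**Working it through.** The plan gives no derived figure to reproduce. The check applies both rules to the SAP's own target days.

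**Inputs.** Target study days come from Sections 16.3.2.1 to 16.3.2.3: OLI Month 12 = 361 and Month 14 = 421; D2I Month 11 = 331 and Month 13 = 391; BIK Month 12 = 337 and Month 13 = 365. The windows' upper bounds are Injection Study Day 372 (OLI), Study Day 372 (D2I) and Study Day 378 (BIK).

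**Formulas.** D1 is the Appendix 1 denominator (start to Snapshot viral load). D2 is the Section 16.6.2 denominator (start to latest Maintenance visit).

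- First excluded whole-day count, Appendix 1: 0.10 × D1, rounded up.
- First excluded whole-day count, Section 16.6.2: 0.10 × D2, rounded down, plus 1.
- Section 16.6.2 limit as a share of time to the endpoint: 0.10 × D2 / D1.

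**Case 1: Month 13/14 visit present, all visits on target day**

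| | D1 | D2 | D2 − D1 | Appendix 1 | 16.6.2 | Days on which the rules differ | 0.10 × D2 / D1 |
|---|---|---|---|---|---|---|---|
| OLI | 361 | 421 | 60 | 36.1 → 37 | 42.1 → 43 | 37–42 | 11.7% |
| D2I | 331 | 391 | 60 | 33.1 → 34 | 39.1 → 40 | 34–39 | 11.8% |
| BIK | 337 | 365 | 28 | 33.7 → 34 | 36.5 → 37 | 34–36 | 10.8% |

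**Case 2: viral load at the upper end of the window.** Assumptions: the first OLI injection is on Study Day 31, so Injection Study Day 372 is Study Day 372 + 30 = 402; in BIK, the visit on Day 378 is also the last.

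| | D1 | D2 | Appendix 1 | 16.6.2 | Gap |
|---|---|---|---|---|---|
| OLI | 402 | 421 | 41 | 43 | 2 days |
| D2I | 372 | 391 | 38 | 40 | 2 days |
| BIK | 378 | 378 | 38 | 38 | 0 days |

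**Case 3: last visit is Month 12/11, on target day.** D2 = D1, and the first excluded counts are 37, 34 and 34 under both rules.

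**The inequality alone.** For the same denominator, at-least-10% and more-than-10% give different whole-day cut-offs only when the denominator is a multiple of 10. That is 12 of the 114 values from 289 to 402, and none of the target-day denominators above.

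**Weight of one participant.** With 654 randomised 2:1, Q2M has about 654 × 2/3 = 436 participants. One Snapshot failure moved in or out is about 1/436 = 0.23 percentage points, or 0.23/4 ≈ 6% of the 4-point margin.

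**The case against.** The strongest reply is that the SAP does have a hierarchy. Sections 4 and 4.1 and the opening of Appendix 1 make Appendix 1 the defining text, and Section 16.6.2 itself points back to Section 16.1. A reader might infer that the plan contains two rules of equal standing and so two PP populations. The documents do not support that: Section 16.6.2 is a subordinate restatement that is wrong in detail. What remains is that it states a complete ratio and cut-off under the heading for compliance, where a programmer may take them from.

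A reader might also infer that more under-dosed Q2M than BIK participants are actually kept. Nothing in the SAP shows that anyone falls in the band, and membership also depends on case-by-case review. The 60 against 28 extra days apply only to participants with a Month 13/14 visit. Reading overall exposure as the Section 16.6.4 quantity is the likely interpretation, but it is not stated.

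Finally, the numerators already differ by arm under Appendix 1: late injection days and related events in Q2M, interruption days in BIK. A common 10% limit is therefore not equal stringency, and the correction does not make it so. It only makes numerator and denominator cover the same period. This objection stands, as does another: Appendix 1 does not say where the denominator ends for a participant with no Snapshot viral load in the window, so a bare cross-reference would leave a gap.

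**Conclusion.** The point holds as a wording error with a limited numerical effect. Section 16.6.2 gives a denominator that can extend beyond the endpoint while the numerator does not, and in participants with a Month 13/14 visit on target days this loosens the limit by 1.7 to 1.8 percentage points in Q2M and 0.8 in BIK. The corresponding bands are 6 days and 3 days wide. They narrow to 2, 2 and 0 days (OLI, D2I, BIK) at the upper end of the viral load window and are essentially nil when the last visit is Month 12/11. The choice between the two inequalities matters only at exactly 10%.

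These figures assume that overall exposure means the Section 16.6.4 definition and, for the target-day case, that visits are on schedule. A reader might infer a threat to the non-inferiority conclusion. That does not follow: the primary analysis uses mITT-E, PP is a sensitivity analysis without its own decision rule, and the 0.23-point shift needs a Q2M participant who is both in the band and a Snapshot failure. The correction is still worthwhile because it costs almost nothing and leaves one reproducible PP rule.

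**What to change.** 1. In Section 16.6.2, delete the percentage, its denominator and the cut-off, and refer to Appendix 1 for the whole non-compliance rule. The choice between the two definitions of overall exposure then no longer bears on the PP set.
2. In Appendix 1, add that for participants with no Snapshot viral load in the window, the denominator ends on the same date as the numerator: the analysis timepoint visit or the date of IP discontinuation or withdrawal, whichever is earlier.
3. If the Month 12 PP set has already been fixed, record which denominator was programmed and whether any participant falls between the two rules.

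The cost is two sentences of SAP text and, if step 3 applies, one listing. No new data and no change to the primary analysis are needed.
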